5.3.5.7 Deaths

All deaths that occur during the protocol-specified adverse event reporting period (see [Section 5.3.1](#)), regardless of relationship to study drug, must be recorded on the Adverse Event eCRF and immediately reported to the Sponsor (see [Section 5.4.2](#)). This includes death attributed to progression of advanced IPF and PH or suspected PH.

Death should be considered an outcome and not a distinct event. The event or condition that caused or contributed to the fatal outcome should be recorded as the single medical concept on the Adverse Event eCRF. Generally, only one such event should be reported. The term "**sudden death**" should be used only for the occurrence of an abrupt and unexpected death due to presumed cardiac causes in a patient with or without preexisting heart disease, within 1 h after the onset of acute symptoms or, in the case of an unwitnessed death, within 24 h after the patient was last seen alive and stable. If the cause of death is unknown and cannot be ascertained at the time of reporting, "**unexplained death**" should be recorded on the Adverse Event eCRF. If the cause of death later becomes available (e.g., after autopsy), "unexplained death" should be replaced by the established cause of death.

If the death is attributed to progression of advanced IPF and PH, "advanced IPF" or "advanced PH" or "suspected IPF progression" or "suspected PH progression" should be recorded on the Adverse Event eCRF.

Deaths that occur after the adverse event reporting period should be reported as described in [Section 5.6](#).

5.3.5.8 Preexisting Medical Conditions

A preexisting medical condition is one that is present at the Screening Visit for this study. Such conditions should be recorded on the General Medical History and Baseline Conditions eCRF.

A preexisting medical condition should be recorded as an adverse event only if the frequency, severity, or character of the condition worsens during the study. When recording such events on the Adverse Event eCRF, it is important to convey the concept that the preexisting condition has changed by including applicable descriptors (e.g., "more frequent headaches").

5.3.5.9 Lack of Efficacy or Worsening of Advanced IPF and PH

Medical occurrences or symptoms of deterioration that are anticipated as part of advanced IPF and PH should be recorded as an adverse event if judged by the Investigator to have unexpectedly worsened in severity or frequency or changed in nature at any time during the study. When recording an unanticipated worsening of advanced IPF and worsening of PH on the Adverse Event eCRF, it is important to convey the concept that the condition has changed by including applicable descriptors (e.g., "worsening of IPF" or "exacerbation of IPF" and "worsening of PH").

5.3.5.10 Hospitalization or Prolonged Hospitalization

Any adverse event that results in hospitalization (i.e., inpatient admission to a hospital) or prolonged hospitalization should be documented and reported as a serious adverse event (per the definition of serious adverse event in [Section 5.2.2](#)), except as outlined below.

Pirfenidone and sildenafil—F. Hoffmann-La Roche Ltd
78/Protocol MA29957, Version 2

The following hospitalization scenarios are not considered to be adverse events:

- Hospitalization for respite care
- Hospitalization for a preexisting condition, provided that all of the following criteria are met:
 - The hospitalization was planned prior to the study or was scheduled during the study when elective surgery became necessary because of the expected normal progression of the disease
 - The patient has not experienced an adverse event

The following hospitalization scenarios are not considered to be serious adverse events, but should be reported as adverse events instead:

- Hospitalization that was necessary because of patient requirement for outpatient care outside of normal outpatient clinic operating hours

5.3.5.11 Adverse Events Associated with an Overdose or Error in Drug Administration

An overdose is the accidental or intentional use of a drug in an amount higher than the dose being studied. An overdose or incorrect administration of study treatment is not itself an adverse event, but it may result in an adverse event. All adverse events associated with an overdose or incorrect administration of study drug should be recorded on the Adverse Event eCRF. If the associated adverse event fulfills seriousness criteria, the event should be reported to the Sponsor immediately (i.e., no more than 24 h after learning of the event; see [Section 5.4.2](#)).

5.3.5.12 Patient-Reported Outcome Data

Adverse event reports will not be derived from patient reported outcome (PRO) data by the Sponsor, and safety analyses will not be performed using PRO data. However, if any PRO responses suggestive of a possible adverse event are identified during site review of the PRO data, the Investigator will determine whether the criteria for an adverse event have been met and, if so, will report the event on the Adverse Event eCRF.

5.4 IMMEDIATE REPORTING REQUIREMENTS FROM INVESTIGATOR TO SPONSOR

Certain events require immediate reporting to allow the Sponsor to take appropriate measures to address potential new risks in a clinical trial. The Investigator must report such events to the Sponsor immediately; under no circumstances should reporting take place more than 24 h after the Investigator learns of the event. The following is a list of events that the Investigator must report to the Sponsor within 24 h after learning of the event, regardless of relationship to study drug:

- Serious adverse events (see [Section 5.4.2](#) for further details)
- Adverse events of special interest (see [Section 5.4.2](#) for further details)
- Pregnancies (see [Section 5.4.3](#) for further details)

The Investigator must report new significant follow-up information for the events above to the Sponsor immediately (i.e., no more than 24 h after becoming aware of the information). New significant information includes the following:

- New signs or symptoms or a change in the diagnosis
- Significant new diagnostic test results
- Change in causality based on new information
- Change in the event's outcome, including recovery
- Additional narrative information on the clinical course of the event

Investigators must also comply with local requirements for reporting serious adverse events to the local health authority and independent review board/ethics committee (IRB/EC).

5.4.1 Emergency Medical Contacts

To ensure the safety of study patients, an Emergency Medical Call Center Help Desk will access the Roche Medical Emergency List, escalate emergency medical calls, provide medical translation service (if necessary), connect the Investigator with a Roche Medical Responsible (listed above and/or on the Roche Medical Emergency List), and track all calls. The Emergency Medical Call Center Help Desk will be available 24 h per day, 7 days per week. Toll-free numbers for the Help Desk, as well as Medical Monitor and Medical Responsible contact information, will be distributed to all Investigators.

5.4.2 Reporting Requirements for Serious Adverse Events and Adverse Events of Special Interest

5.4.2.1 Events That Occur prior to Study Drug Initiation

After informed consent has been obtained all adverse events should be reported. The Serious Adverse Event/Adverse Event of Special Interest Reporting Form provided to Investigators should be completed and submitted to the Sponsor or its designee immediately (i.e., no more than 24 h after learning of the event), either by faxing or by scanning and emailing the form using the fax number or email address provided to Investigators.

5.4.2.2 Events That Occur after Study Drug Initiation

After initiation of study drug, serious adverse events and adverse events of special interest will be reported until 28 days after the last dose of study drug. Investigators should record all case details that can be gathered immediately (i.e., within 24 h after learning of the event) on the Adverse Event eCRF and submit the report via the electronic data capture (EDC) system. A report will be generated and sent to Roche Safety Risk Management from the EDC system.

In the event that the EDC system is unavailable, the Serious Adverse Event/Adverse Event of Special Interest Reporting Form provided to Investigators should be completed

and submitted to the Sponsor or its designee immediately (i.e., no more than 24 h after learning of the event), either by faxing or by scanning and emailing the form using the fax number or email address provided to Investigators. Once the EDC system is available, all information will need to be entered and submitted via the EDC system.

Instructions for reporting post-study adverse events are provided in [Section 5.6](#).

5.4.3 Reporting Requirements for Pregnancies

5.4.3.1 Pregnancies in Female Patients

Female patients of childbearing potential will be instructed to immediately inform the Investigator if they become pregnant during the study or within 12 weeks after the last dose of study drug. A Clinical Trial Pregnancy Reporting Form should be completed and submitted to the Sponsor or its designee immediately (i.e., no more than 24 h after learning of the pregnancy), either by faxing or by scanning and emailing the form using the fax number or email address provided to Investigators. Pregnancy should not be recorded on the Adverse Event eCRF. The Investigator should discontinue study drugs and counsel the patient, discussing the risks of the pregnancy and the possible effects on the fetus. Monitoring of the patient should continue until conclusion of the pregnancy. Any serious adverse events associated with the pregnancy (e.g., an event in the fetus, an event in the mother during or after the pregnancy, or a congenital anomaly/birth defect in the child) should be reported on the Adverse Event eCRF. In addition, the Investigator will submit a Clinical Trial Pregnancy Reporting Form when updated information on the course and outcome of the pregnancy becomes available.

5.4.3.2 Pregnancies in Female Partners of Male Patients

Male patients will be instructed through the Informed Consent Form to immediately inform the Investigator if their partner becomes pregnant during the study or within 118 days (17 weeks) after the last dose of study drug. A Clinical Trial Pregnancy Reporting Form should be completed and submitted to the Sponsor or its designee immediately (i.e., no more than 24 h after learning of the pregnancy), either by faxing or by scanning and emailing the form using the fax number or email address provided to Investigators. Attempts should be made to collect and report details of the course and outcome of any pregnancy in the partner of a male patient exposed to study drug. The pregnant partner will need to sign an Authorization for Use and Disclosure of Pregnancy Health Information to allow for follow-up on her pregnancy. After the authorization has been signed, the Investigator will submit a Clinical Trial Pregnancy Reporting Form when updated information on the course and outcome of the pregnancy becomes available. An Investigator who is contacted by the male patient or his pregnant partner may provide information on the risks of the pregnancy and the possible effects on the fetus, to support an informed decision in cooperation with the treating physician and/or obstetrician.

5.4.3.3 Abortions

Any abortion should be classified as a serious adverse event (as the Sponsor considers abortions to be medically significant), recorded on the Adverse Event eCRF, and reported to the Sponsor immediately (i.e., no more than 24 h after learning of the event; see [Section 5.4.2](#)).

5.4.3.4 Congenital Anomalies/Birth Defects

Any congenital anomaly/birth defect in a child born to a female patient exposed to study drug, or the female partner of a male patient exposed to study drug, should be classified as a serious adverse event, recorded on the Adverse Event eCRF and reported to the Sponsor immediately (i.e., no more than 24 h after learning of the event; see [Section 5.4.2](#)).

5.5 FOLLOW-UP OF PATIENTS AFTER ADVERSE EVENTS

5.5.1 Investigator Follow-Up

The Investigator should follow each adverse event until the event has resolved to baseline grade or better, the event is assessed as stable by the Investigator, the patient is lost to follow-up, or the patient withdraws consent. Every effort should be made to follow all serious adverse events considered to be related to study drug or trial-related procedures until a final outcome can be reported.

During the study period, resolution of adverse events (with dates) should be documented on the Adverse Event eCRF and in the patient's medical record to facilitate source data verification.

All pregnancies reported during the study should be followed until pregnancy outcome.

5.5.2 Sponsor Follow-Up

For serious adverse events, adverse events of special interest, and pregnancies, the Sponsor or a designee may follow up by telephone, fax, electronic mail, and/or a monitoring visit to obtain additional case details and outcome information (e.g., from hospital discharge summaries, consultant reports, autopsy reports) in order to perform an independent medical assessment of the reported case.

5.6 ADVERSE EVENTS THAT OCCUR AFTER THE ADVERSE EVENT REPORTING PERIOD

The Sponsor should be notified if the Investigator becomes aware of any serious adverse event that occurs after the end of the adverse event reporting period (defined as 28 days after the last dose of study drug), if the event is believed to be related to prior study drug treatment. These events should be reported through use of the Adverse Event eCRF. However, if the EDC system is not available, the Investigator should report these events directly to the Sponsor or its designee, either by faxing or by scanning and

emailing the Serious Adverse Event/Adverse Event of Special Interest Reporting Form using the fax number or email address provided to Investigators.

5.7 EXPEDITED REPORTING TO HEALTH AUTHORITIES, INVESTIGATORS, INSTITUTIONAL REVIEW BOARDS, AND ETHICS COMMITTEES

The Sponsor will promptly evaluate all serious adverse events and adverse events of special interest against cumulative product experience to identify and expeditiously communicate possible new safety findings to Investigators, IRBs, ECs, and applicable health authorities based on applicable legislation.

To determine reporting requirements for single adverse event cases, the Sponsor will assess the expectedness of these events using the following reference document(s):

- Pirfenidone Investigator's Brochure
- US Prescribing information (USPI) for Sildenafil

The Sponsor will compare the severity of each event and the cumulative event frequency reported for the study with the severity and frequency reported in the applicable reference document.

Reporting requirements will also be based on the Investigator's assessment of causality and seriousness, with allowance for upgrading by the Sponsor as needed.

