4.3.2.5 Dose Modification or Discontinuation

The Investigator will be responsible for monitoring patients as frequently as clinically indicated for treatment-emergent adverse events or other toxicities, and for doing so in a manner consistent with the instructions in the labels for pirfenidone, sildenafil, and any other medications used to treat a study patient. The Investigator may contact the Medical Monitor or designee to discuss dose modification or discontinuation of study treatment. All treatment-emergent adverse events and toxicities will be followed according to procedures in this protocol. If a patient experiences a clinically significant treatment-emergent adverse event or toxicity, treatment of symptoms and/or temporary dose reduction, interruption, or discontinuation of study treatment should be considered. All changes in dosing will be recorded by the patient in the patient diary and by the study center in the electronic eCRF.

If a patient is hospitalized for any reason, the Investigator should consider continuing the study treatment if appropriate. If the patient is hospitalized at an institution that is not affiliated with the study center, the Investigator is encouraged to discuss study participation with the treating physician at the earliest possible time. All records pertaining to the hospitalization should be obtained by the study center. The Investigator will be responsible for determining the reason for hospitalization (admission to the hospital) (respiratory, cardiac, other), distinguishing elective from non-elective hospitalization, and determining the cause of death (respiratory, cardiac, other). The sections below identify events that require interruption/discontinuation of study treatment, and provide guidance for modifying doses, restarting treatment after an interruption.

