4.5.15 Patient Study Discontinuation

Patients have the right to voluntarily withdraw from the study at any time for any reason. In addition, the Investigator has the right to withdraw a patient from study at any time. Reasons for withdrawal from the study may include, but are not limited to, the following:

- Patient withdrawal of consent at any time
- Any medical condition that the Investigator or Sponsor determines may jeopardize the patient's safety if he or she continues in the study
- Lung transplantation
- Investigator or Sponsor determines it is in the best interest of the patient

Every attempt should be made to keep patients on study treatment throughout the duration of the trial.

Every effort should be made to obtain information on patients who withdraw from the study. The primary reason for withdrawal from the study should be documented on the appropriate eCRF. However, patients will not be followed for any reason after consent has been withdrawn. Patients who withdraw from the study will not be replaced.

The Investigator should show due diligence and explore all possible options to reach a patient who fails to attend a visit. The site must document all attempts to contact the patient in the medical records / source documents.

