4.5.16 Patient Study Treatment Discontinuation

Patients must discontinue study treatment (sildenafil and/or pirfenidone) if they experience any of the following (see also [Sections 5.1.1](#) and [5.1.2](#)):

- Inability to tolerate study treatment after efforts have been made to gain tolerability
- An elevation in liver test results of the magnitude described below
- Use of a prohibited investigational therapy or concomitant medication
- Sildenafil/placebo will be stopped in patients with acute coronary syndromes, atrioventricular AV block, life-threatening arrhythmias, left ventricular dysfunction (ejection fraction <25%), or clinically significant visual changes
- Pregnancy
- Signs or symptoms of angioedema
- Any other treatment-emergent adverse event or toxicity that is unacceptable in the opinion of the patient or Investigator

Sildenafil/placebo will be stopped (temporarily or permanently) in any patient with systolic blood pressure (SBP) <100 mmHg or diastolic blood pressure (DBP) <50 mmHg.

The primary reason for study treatment discontinuation should be documented on the appropriate eCRF. Patients who discontinue study treatment prematurely will not be replaced.

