5.3.1 Adverse Event Reporting Period

Investigators will seek information on adverse events at each patient contact. All adverse events, whether reported by the patient or noted by study personnel, will be recorded in the patient's medical record and on the Adverse Event eCRF.

After informed consent has been obtained all adverse events should be reported (see [Section 5.4.2](#) for instructions for reporting serious adverse events) until 28 days after the last dose of study drug. Instructions for reporting adverse events that occur after the adverse event reporting period are provided in [Section 5.6](#).

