6.4.1 Primary Efficacy Endpoint

The primary efficacy objective for this study is to evaluate the efficacy of adding sildenafil compared with placebo to pirfenidone treatment in patients with advanced IPF and *risk* of Group 3 PH.

The primary efficacy endpoint will be evaluated based on a comparison of the proportion of patients showing disease progression over 52 weeks of treatment period, as evidenced by reaching the following combined endpoint:

- Relative decline in 6MWD of at least 15% from baseline (as defined below*), respiratory-related non-elective hospitalization, or all-cause mortality

* Relevant decline in 6MWD from baseline is defined as:

- Any decline >25% from baseline or
- A decline between 15-25% from baseline, if accompanied by at least one of the following:
 - worsening of SpO₂ desaturation during the 6MWT compared to baseline

- worsening of the maximum Borg scale during the 6MWT compared to baseline
- increased O₂ requirements during the 6MWT compared to baseline.

The primary analysis will be based on the ITT population, defined as all randomized patients. Patients who discontinue treatment prematurely will be analyzed based on the available data. No imputation method will be applied. Patients who undergo lung transplantation during the study will be withdrawn from the study at the time of hospitalization for transplantation. *In addition, sensitivity analysis of the primary endpoint will be performed. The details of those analyses will be provided in the Statistical Analysis Plan.*

The primary analysis of the primary endpoint will compare disease progression rates in each treatment arm using a Chi-square test with a one-sided significance level $\alpha = 0.05$.

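### The explicit reporting rules for deaths and serious events stop 28 days after the last dose of an undefined 'study drug' and then filter on relatedness, and no passage requires endpoint collection to week 52 after treatment is stopped

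*Protocol*

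**What the plan says.** **Endpoint.** Section 6.4.1 compares the proportion of patients who progress over 52 weeks, where progression is a relevant 6MWD decline, a respiratory-related non-elective hospitalisation or death from any cause. The population is everyone randomised. "Patients who discontinue treatment prematurely will be analyzed based on the available data", and no imputation is applied.

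**Reporting rules.**
- Section 5.3.1: adverse events are reported from consent "until 28 days after the last dose of study drug".
- Section 5.4.2.2: "serious adverse events and adverse events of special interest will be reported until 28 days after the last dose of study drug".
- Section 5.3.5.7: deaths within that period are recorded regardless of relationship. "Deaths that occur after the adverse event reporting period should be reported as described in" Section 5.6.
- Section 5.6: after the period, the sponsor is notified of a serious event if the investigator becomes aware of it and "if the event is believed to be related to prior study drug treatment".

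**Passages that point to wider collection.**
- Section 4.3.2.5, on hospitalised patients: "All records pertaining to the hospitalization should be obtained by the study center". The investigator also classifies the reason for admission, elective or non-elective status, and cause of death.
- Section 4.5.15: "Every effort should be made to obtain information on patients who withdraw from the study". Sites must also try to reach patients who miss a visit.
- Section 6: the primary analysis follows completion by all patients of the 52-week phase and the 4-week Follow-up visit.
- Sections 3.2 and 6.5 and the Adverse Events row of Appendix 1: adverse events and deaths are collected into an additional safety follow-up.

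**Stopping treatment.** Section 4.5.16 deals with treatment discontinuation separately from study withdrawal (Section 4.5.15). On data collection it says "The primary reason for study treatment discontinuation should be documented on the appropriate eCRF", and nothing about later visits. Appendix 1 puts early study withdrawal and treatment discontinuation in one column.

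**The concern.** The endpoint is tied to randomisation and to a fixed 52 weeks. The explicit reporting rules are tied to the last dose and, after 28 days, to a causality opinion. A relatedness filter does not suit an endpoint that counts death from any cause.

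Take a patient who stops both drugs at month 3, no longer attends, and dies of an unrelated cause at month 9. That death is a primary-endpoint event, but the reporting rules do not require it to be recorded. With available data and no imputation, such a patient may be counted as not having progressed. If stopping differs between arms, the loss differs too. The analysis plan cannot repair this, because it can use only what sites were asked to collect.

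**Working it through.** **1. Length of the uncovered period.** Inputs: window of 28 days after last dose (Section 5.3.1); week 52 visit on day 365 (Appendix 1). Uncovered days = 365 − (day of last dose + 28).

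| Last dose on day | Uncovered days |
|---|---|
| 45 | 365 − 73 = 292 |
| 90 | 365 − 118 = 247 |
| 180 | 365 − 208 = 157 |
| 270 | 365 − 298 = 67 |
| 337 or later | 0 |

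**2. Who is affected.** Section 4.3 defines 'study treatments' as pirfenidone, sildenafil and placebo; 'study drug' has no definition. Section 4.2 uses it for the blinded product, Section 4.3.2.1 for pirfenidone, Section 4.3.2.2 for sildenafil/placebo, and Section 4.3.4 for pirfenidone. A patient who stops both drugs falls outside the window on any reading. A patient who stops only sildenafil/placebo falls outside it only if the term means the blinded product.

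**3. Do the other passages close the gap?**
- Sections 4.3.2.5 and 4.5.15 set no 28-day cut-off, but neither sets a period or says that collection runs to week 52.
- The additional safety follow-up starts after the week 56 visit, so it does not secure events before week 52 in early stoppers.
- The Adverse Events row covers every visit, but no passage says that off-treatment patients keep attending. A site can read the merged column as an exit visit.
- Section 3.1 encourages completion for patients with a 6MWD or hospitalisation event, not for those who stop treatment.

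**4. Illustration of size.** The plan's own figure first: 72% vs 54%, one-sided 5%, 80% power, no continuity correction gives 88 per arm, 176 in total, as stated in Section 6.1.

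Assumptions not in the document: the stopping rates; stopping time uniform over 52 weeks; constant hazard; no composite event seen later than 4 weeks after last dose; unseen events counted as non-progression.

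- Hazard h = −ln(1 − p)/52: 0.02448 per week at p = 0.72 and 0.01493 at p = 0.54.
- Share of stoppers with an unseen event = average over s from 0 to 52 of [exp(−h·min(s + 4, 52)) − exp(−52h)]: 0.2339 at 72% and 0.1961 at 54%.
- Observed rate = true rate − stopping rate × unseen share. Example, 10% stopping at 72%: 0.72 − 0.10 × 0.2339 = 0.697.
- Error and power: exact binomial, 88 per arm, pooled z, one-sided 0.05. Error is under 72% in both arms; power is for 72% vs 54%.

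| Stopping, placebo / sildenafil | Error | Power |
|---|---|---|
| None | 5.1% | 80.4% |
| 10% / 10% | 5.0% | 78.5% |
| 20% / 20% | 4.9% | 76.7% |
| 5% / 10% | 7.1% | not a loss |
| 10% / 20% | 9.4% | not a loss |
| 20% / 10% | 2.4% | 67.8% |

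If half of the later events are captured, the 7.1% and 9.4% become 6.0% and 7.1%, and the 67.8% becomes 74.4%. Equal stopping costs a little power and leaves the error near 5%; the error moves only when stopping is unequal.

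**The case against.** The strongest reply is that these are safety-reporting rules, not limits on endpoint data. Section 4.3.2.5 asks for hospital records and a cause of death with no cut-off; Section 5.1 has hospitalisations and all-cause mortality reviewed by the iDMC; Section 5.3.1 seeks adverse events at each patient contact; Section 4.5.15 asks sites to pursue missed visits; and Section 6 assumes that patients reach the Follow-up visit. A patient who stops treatment but keeps attending would have events recorded. Section 5.3.4 assesses causality for each therapy, which suggests that 'study drug' covers both products, so that a patient still on pirfenidone stays inside the window.

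Much of this stands. A reader might infer that the 28-day rule is the only stated period for collecting these events. It is not: Sections 3.2 and 6.5 and Appendix 1 also provide for adverse-event and death collection. A reader might also infer that every patient who stops both drugs is bound to be lost. That does not follow either, because leaving the study and stopping treatment are treated separately and a diligent site may go on collecting.

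The objection to the numbers also stands. The model removes 6MWD declines, which a reporting rule for deaths and serious events does not govern. It counts unseen events as non-progression, which the protocol does not state. No passage supports a twofold difference in stopping between arms.

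What the objection does not supply is a sentence requiring endpoint collection to week 52 after treatment is stopped.

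**Conclusion.** The point holds as a conflict to be reconciled, and it should be fixed. The explicit reporting rules end 28 days after an undefined last dose and then filter on relatedness; the endpoint runs to week 52 regardless of treatment or causality; and the passages that lean towards wider collection do not bridge the two. The exposed group is patients who stop both drugs early and do not keep attending, plus those who stop only sildenafil/placebo if 'study drug' means the blinded product.

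The document gives no stopping rate, so neither the size nor the direction of any bias can be derived. The error and power figures are illustration only and do not carry the conclusion. Confidence is medium, because actual practice depends on how sites read the passages together.

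**What to change.** - State that all deaths and all non-elective hospitalisations, with cause, up to week 52 are recorded as endpoint data for every randomised patient who has not withdrawn consent, irrespective of relatedness or time since last dose. Cross-refer to this from Sections 5.3.1, 5.3.5.7, 5.4.2.2 and 5.6, and bring Sections 3.2, 4.3.2.5, 4.5.15, 6 and 6.5 into line.
- State in Section 4.5.16 and Appendix 1 that patients who stop treatment but not the study keep the visit and 6MWT schedule to week 52. Give treatment discontinuation and study withdrawal separate columns in Appendix 1.
- Define 'last dose of study drug' and use it consistently.

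The cost is protocol wording and a small added visit or contact burden for off-treatment patients and their sites. The sample size and the primary test are unchanged.
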